### CBM-I is a simple, efficient, and effective, method to engage interpretation bias.

The current proposal aims to develop an efficient and scalable method for engaging interpretation bias to improve outcomes during and following hospitalization. Cognitive bias modification tasks targeting interpretation bias (CBM-I) are low-intensity, computerized interventions that facilitate a more adaptive interpretive style via repeated practice on a training task. Importantly, the CBM-I task proposed here aims to engage interpretation bias in an “on-line” manner - the moment of encountering ambiguity - which more closely matches the manner that interpretation bias naturally operates and may not require as much insight as alternative methods. The proposed intervention, called **HabitWorks**, uses a **Word-Sentence Association**

**Paradigm (WSAP)** to reinforce an adaptive interpretation style. Specifically, this task presents a word representing either a negative or benign interpretation (“criticize” or “praise”) of an ambiguous sentence that follows (“Your boss wants to meet with you”). Individuals then indicate by button press if they think the word is related to the sentence. The feedback, “You are correct!” is displayed if they endorse benign interpretations or reject negative ones (Figure 1). This task taxes

attentional control and working memory to remember the word that flashes and make the relatedness judgment. Participants complete the task as quickly and as accurately as possible, thereby prompting more automatic responding.

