Demog. Form, CEQ	X				
PHQ-9; GAD-7	X	X	X	X	X
Q-LES-Q, BHS, CFI, MPS, GSE	X		X	X	X
Exit Questionnaire				X	
WSAP	X	X	X	X	X
Scenario Recognition Task				X	
EMA PANAS	X	X	X	X	X
CSSRS- Self Report	X			X	X
System Usability Scale- HW condition				X	
TWEETS- HW condition				X	

The Scenario recognition task is the most widely used assessment of interpretation bias in CBM- and will ensure that effects are not solely attributable to practice or method effects. In brief, participants first read 10 ambiguous scenarios and a comprehension question to ensure they actually read the scenario. In the second phase, participants read the title of the ambiguous scenario followed by four versions of the final sentence presented in a random order. Sentences represent a) a possible positive interpretation, b) a possible negative interpretation, c) a positive foil, and d) a negative foil.

Participants rate each sentence for its similarity in meaning to the original story using a 4-point scale ranging from 1 (very different in meaning) to 4 (very similar in meaning). We will calculate the average similarity rating for negative and positive interpretations.

Co-primary clinical outcomes will include stake-holder relevant measures of global improvement and functioning. The PI will train study staff to administer these brief scales and will monitor reliability using established procedures at the BHP.

Clinician-administered Clinical Global Improvement Scale (CGIS) to assess global improvement.

Clinician-rated 5-item Work and Social Adjustment Scale (WSAS) to assess interference caused by the patient's symptoms in the domains of work, home management, leisure, and family relationships.

Other self-report measures will include:

Credibility Expectancy Questionnaire to assess patients' beliefs about the treatment expectancy (affectively based) and treatment rationale credibility (cognitively based).

Exit Questionnaire to assess patients' satisfaction with the treatment provided.

Beck Hopelessness Scale (BHS) to assess negative attitudes about the future.

Cognitive Flexibility Inventory: The Cognitive Flexibility Inventory is a measure of mental flexibility and assesses the degree to which individuals are able to replace maladaptive thoughts with adaptive ones and maintain a balanced mindset.

15-Item Multidimensional Perfectionism Scale (short form): The MPS is a widely used self-report measure of perfectionism.

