### Phase 2: Open Trial

The primary aims of this treatment development project are to develop: a) HabitWorks, b) procedures for hospital augmentation and bridge to outpatient care, and c) procedures for a subsequent RCT. First, we will analyze qualitative data obtained from post-treatment interviews and exit questionnaire. The PI will content analyze audio recordings using a rapid coding technique. Audio recordings will then be transcribed verbatim and analyzed with more conventional analytic methods. Using the constant comparison method from grounded theory transcripts will be read for emerging themes. After independently categorizing thematic clusters, the scientific team will create a coding scheme to organize data, prepare a written report detailing the emerging themes, and discuss results with the advisory board.

We will compare outcomes to a **priori target outcomes** (see Table) after each iteration of the open trial. We will calculate descriptive statistics (e.g., mean, frequencies) to evaluate whether the target outcome was met. When the target is not met, this will prompt a discussion with the team and advisory board about potential modifications. We will calculate effect size estimates to characterize pre-post differences (open trial) and the associated 95% CIs, to understand the precision, or lack thereof, of our estimates.

Target Outcomes	
Target Engagement:	75% of HabitWorks group moves into normal range  of interpretation bias (Benign endorsement = 70%; Negative endorsement = 30%) on the WSAP and on the Scenario Recognition Task ( Similarity rating (1 to 4) for target sentences: benign = 2.3; negative = 1.9).
Treatment Credibility & Expectancy:	Average = 5 (moderate credibility or 50% expectancy)
Retention:	75% of participants complete the 3 month-assessment 75% of participants complete HabitWorks daily during acute treatment 50% of participants complete HabitWorks 3x week in transition phase
Satisfaction:	Average rating 5 or above (on a 1 to 7 scale) on the Exit Questionnaire
Treatment response:	50% of HabitWorks group responds to treatment (“much or very much improved” on CGIS) and 20% reduction in functional impairment in HabitWorks group with a clinically meaningful between group effect size of $d = .40$

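### The Scenario Recognition Task collects foil ratings but is scored on target sentences only, so it cannot separate changed interpretation from a general shift towards positive and away from negative sentences.

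*Protocol*

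**What the plan says.** The Protocol (Study Procedures, Measures) describes the task as follows. There are 10 scenarios, each with four sentences to rate: "Sentences represent a) a possible positive interpretation, b) a possible negative interpretation, c) a positive foil, and d) a negative foil". Foils are rated like targets: "Participants rate each sentence for its similarity in meaning to the original story using a 4-point scale". One scoring sentence follows: "We will calculate the average similarity rating for negative and positive interpretations". Since the sentence list separates interpretations from foils, this means the two target types.

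The SAP's Target Outcomes table (Phase 2: Open Trial) agrees. Its engagement goal, "75% of HabitWorks group moves into normal range", applies to the WSAP and to this task, with the range given as "Similarity rating (1 to 4) for target sentences: benign = 2.3; negative = 1.9".

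The Protocol states why a second bias task is included: it "will ensure that effects are not solely attributable to practice or method effects". The Background describes what the training reinforces: positive feedback "is displayed if they endorse benign interpretations or reject negative ones".

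The Phase 3 Measures section keeps the Open Trial measures unchanged, and the Phase 3 section of the SAP adds between-group effect sizes with 95% CIs. The Schedule of Assessments marks this task at 1 month only. After the foils are described, neither document mentions a foil score, a target-minus-foil contrast or a foil check.

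**The concern.** Target engagement is Aim 2(a), and this is the one interpretation-bias task in the plan whose format HabitWorks does not train. Its value lies in showing that an effect is more than skill at the trained task.

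The method effect most relevant here is a general response habit: accept what is positive, reject what is negative. HabitWorks rewards that pattern daily in the acute phase and three times a week for the following month. Symptom Tracking does not practise it, so if the habit carried over to this task it would not cancel between arms. It would raise the positive target rating and lower the negative one, which is exactly what the planned score counts as healthier interpretation. It would also move the foils, and a change confined to interpretation would not. The foils are therefore what separates the two explanations, and the plan does not use them.

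At stake is how an arm difference on this task can be described when the pilot is used to support the larger trial.

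**Working it through.** **Inputs from the documents.** 10 scenarios × 4 sentences = 40 ratings, of which 20 are foils. Scale 1 to 4. Normal range: benign target 2.3, negative target 1.9. The SAP prints no direction; I assume benign ≥ 2.3 and negative ≤ 1.9. The benchmarks come from cited sources, so there is no figure to reproduce. The documents give no means, SDs or correlations for this task.

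**Step 1: the rule applied to constructed records (only the direction is assumed).** PT, NT = positive and negative target; PF, NF = positive and negative foil. Foil-corrected index = (PT − NT) − (PF − NF).

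| Record | PT | NT | PF | NF | In range? | PT − PF | NT − NF | Index |
|---|---|---|---|---|---|---|---|---|
| A | 2.3 | 1.9 | 2.3 | 1.9 | yes | 0 | 0 | 0 |
| B | 2.3 | 1.9 | 1.5 | 1.5 | yes | 0.8 | 0.4 | 0.4 |
| C | 4 | 1 | 4 | 1 | yes | 0 | 0 | 0 |

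A and B are identical under the planned score. A and C show no target-specific signal, yet both are in range. This is the core of the point.

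**Step 2: a uniform valence shift (baseline assumed).** Start at PT 2.0, NT 2.4, PF 1.6, NF 1.8, which is out of range. Add s to both positive sentences and subtract s from both negative ones. At s = 0.5 the values are 2.5, 1.9, 2.1 and 1.3, which is in range. PT − PF stays at 2.0 − 1.6 = 2.5 − 2.1 = 0.4. NT − NF stays at 2.4 − 1.8 = 1.9 − 1.3 = 0.6.

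**Step 3: how many would be classed in range (all inputs assumed).** Person-level target means are bivariate normal with correlation −0.3 and SD 0.4 to 0.6. The share is P(benign + s ≥ 2.3 and negative − s ≤ 1.9).

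| Unshifted means (benign/negative) | s = 0 | s = 0.4 |
|---|---|---|
| 2.0 / 2.3 | 6–11% | 33–35% |
| 2.1 / 2.2 | 10–16% | 40–46% |
| 1.9 / 2.5 | 2–7% | 20–23% |

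At the largest shift tried here, 0.6, the highest share is 67.5% (means 2.1/2.2, SD 0.4). A separate simulation of discrete ratings used the Step 2 baseline, rating SD 0.8 and person SD 0.3. It gave 4% at s = 0, 38% at 0.5, 67% at 0.75 and 87% at 1.0. In that simulation, passing 75% on this task took a shift of more than 0.75 points on a scale 3 points wide. That the shift leaves target minus foil unchanged (apart from scale-floor effects) is built into these set-ups and is not evidence that such a shift happens.

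**Step 4: whether another planned element covers the gap.**
- The WSAP, also part of the goal, is the trained format. Its description has no foils, and the same habit satisfies its endorsement criterion.
- The comprehension question checks that the scenario was read, not how valence affects ratings.
- With the task at 1 month only, there is no baseline on it. Within-person change cannot be measured, with or without foils; a between-arm comparison at 1 month can.

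**The case against.** The strongest reply is that no bias has been demonstrated. HabitWorks trains a speeded yes/no judgement with feedback; this task asks for graded similarity ratings against a scenario read earlier, and no feedback is mentioned. The habit would have to transfer across formats, and act equally on targets and foils, to produce the pattern in Steps 2 and 3. The documents give no evidence on either. That stands. A reader might infer that the planned comparison is biased towards HabitWorks; the documents support only that the planned score cannot exclude this.

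A reader might also infer that the habit alone would deliver the engagement goal. The figures do not support that: at shifts up to 0.6 the share stays below 75%, and the goal requires the WSAP as well.

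Nor do the documents say that the foils will be discarded. The task description is labelled as brief, the ratings are kept, and the cited sources may describe a foil score. That stands too, but no use of the foils is written down.

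Finally, the stated purpose is modest: effects should not be solely due to practice or method. A different format with a comprehension check partly serves it, and WSAP reaction-time scores add something beyond endorsement. In a descriptive pilot whose co-primary clinical outcomes are the CGIS and WSAS, this limits how much depends on the point. It does not remove it, because the information needed is already collected.

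**Conclusion.** The point holds as a limit on what the planned score can show. With target sentences alone, changed interpretation and general valence responding give the same result; records A and B make this exact, and the assumed direction of the cut-offs is the only input not in the documents. Whether general valence responding occurs in this trial is unknown, and any advantage to HabitWorks depends on its occurring and being stronger in that arm.

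The percentages in Step 3 are illustrations, not predictions. The 2.3 and 1.9 benchmarks are not themselves shown to be wrong. The matter is a worthwhile, inexpensive improvement to the measurement of Aim 2(a), and does not affect the clinical outcomes.

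**What to change.** In the Protocol's description of the task, and in the Phase 3 section of the SAP:

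- Report mean foil ratings by arm and valence beside the target means at 1 month.
- Pre-specify the between-arm difference in target minus foil, separately for positive and negative sentences, each with its 95% CI.
- Keep the 2.3 and 1.9 target-sentence benchmarks as planned.
- State that an arm difference on targets alone will be described as not separated from general valence responding unless the target-minus-foil contrast supports it.

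**Cost.** A few sentences and no new data. The price is precision. If a target mean and a foil mean each average 10 ratings with independent error, the error SD of their difference is √2 ≈ 1.4 times that of the target mean. With 64 to 84 participants split evenly and all assessed, the 95% CI half-width for an arm difference, in SD units of the contrast, is about 1.96 × √(2/32) = 0.49 to 1.96 × √(2/42) = 0.43. It will be wider in practice because the 1-month assessment is optional. The contrast should therefore be read as an estimate with its interval, not as a pass/fail gate.

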**Ecological Momentary Assessment (EMA)**

We will pilot the use of EMA to assess fluctuations in positive and negative affect using the PhenX Toolkit recommended measure PANAS-X. During the 1-month transition phase, participants will complete the PANAS-X 4 times every day via the smartphone app. The surveys will be administered at random times during each one of 4 stratified blocks of time (9am-12pm, 12-3pm, 3-6pm, 6-9pm).

Other interview measures will include:

The Longitudinal Interval Follow-Up Evaluation (LIFE) to assess psycho-pharmacotherapy use, including any medication or dosage changes.

Study staff will conduct a qualitative exit interview with prompts about overall patient experiences, acceptability and feasibility, relevance of the stimuli, and user-experience of the app.

Treatment adherence. Number of sessions completed will be recorded by the app and will be used as both a measure of feasibility/ acceptability, and as needed as a control variable in analyses.

**Compensation**. Participants will receive compensation for their time to complete assessments. Participants will receive \$20 for the eligibility assessment and pretreatment assessment, and an additional \$20 for the post-treatment assessments. They will receive \$30 for the 1-month and 3-month follow-up assessments, \$30 for completing at least 80% of the EMA surveys each week for 1 month, and \$20 for the post-treatment qualitative interview (open trial only).

### **Phase 3: Randomized Controlled Trial**

We will recruit 84 participants for the RCT with optional assessments at pre-, post-, 1-month and 3-month timepoints. Follow-up assessments at the 1-month and 3-month timepoints will be considered optional for participants. In this RCT we will randomize individuals to receive the experimental condition HabitWorks or a Symptom Tracking condition. Those in the HabitWorks group will complete the CBM task via smartphone application as an augmentation to treatment as usual (TAU), while those in the Symptom Tracking Group will complete weekly symptom monitoring surveys as an augmentation to TAU.

### **Procedures under existing protocol:**

All procedures under existing BHP protocol are remaining the same as the Open Trial, except for the changes in the inclusion criteria that eliminates the PHQ-9 item 9 score <2 requirement and restricts additional recruitment to BIPOC participants with the goal of reaching our proposed percentage of BIPOC participants.

**Procedures for Proposed Protocol:**

The research coordinator or another member of the study staff will approach potentially eligible patients (scoring above a 9 on PHQ-9 or GAD-7) on their second day in the program and inform them about the study, and send them a brief screening survey to assess initial eligibility prior to study consent and enrollment (i.e., owns an iPhone, willing to sign a release of information for outpatient providers, willing to use the app per protocol and willing to complete follow-up assessments). If patients are eligible based on this initial screening questionnaire, they will then receive a detailed description of the study procedures, risk, and benefits and will review a study fact sheet for remote consent with trained study staff. Additionally, those patients who did not originally consent to the BHP main study, will have to consent to the main study in order to be eligible for the RCT. They will then complete the interpretation bias assessment to determine eligibility to participate in the trial.

On patients' second day at the BHP, staff will offer participation. Interested patients will complete the eligibility assessment. Study staff will immediately review scores on the measure of interpretation bias (WSAP; see Measures) to determine eligibility. If eligible, they will complete the remaining pre-assessment measures. If ineligible, patients will be compensated and continue with treatment as usual at the BHP. After the eligibility session, patients will be randomized into either HabitWorks or Symptom Tracking groups by the PI.

The PI will train research staff to orient patients to HabitWorks and Symptom Tracking conditions and reinforce the rationale and instructions provided in instructional videos.

**HabitWorks**

Participants assigned to HabitWorks will complete the same procedures as outlined in the Open Trial. Specifically, participants will complete a task designed to improve interpretation biases. During each session, participants complete the previously validated word-sentence association paradigm (~10 min). The task presents ambiguous sentences (“You failed an exam”) and provides positive feedback (“you are correct!”) when participants endorse benign interpretations/attributions (“difficult test”) and negative feedback (“you are incorrect!”) for negative interpretations/attributions (“stupid”). Sessions during the transition phase are shorter (~5 min).

Once enrolled, participants will be asked to complete HabitWorks daily on their smart phones in a quiet room while attending the partial hospital, at least three times per week at home for 1-month following discharge, and as desired during the final 2 months. During the 1-month post-acute period, participants may complete assessments of symptoms (PHQ-9 and GAD-7) as often as desired, including optional once weekly check-ins for the study. For people in the HabitWorks condition, these surveys are administered via the HabitWorks app.

During the 1-month post-discharge period, participants will also complete daily assessment of affect (see EMA description in Measures). These surveys will be administered via Metricwire. The HabitWorks and Metricwire app was designed to protect participants' privacy, confidentiality, and data security. Only research personnel will have access to study information. Data collected by the Metricwire app is encrypted, and downloaded by the researcher to the local research server in a de-identified format (i.e., subject ID number). The local research server is only accessible by study staff. Study staff will provide orientation to the app and answer any questions regarding the assessments and data collected.

HabitWorks Treatment phase	Location	Frequency of sessions	Duration
---------------------------------------	-----------------	------------------------------	-----------------

Acute (1 to 14 days)	Hospital	Daily to augment CBT-based hospital treatment	10 min
Transition (1-month)	Home	3x per week to transition from intensive hospital to outpatient care, 4x daily affect surveys, weekly symptom monitoring survey	15 min/day
Long-Term (2 mo)	Home	Sessions completed as desired by individual	5 min

### Symptom Tracking

Participants assigned to the Symptom Tracking condition will be presented with a treatment rationale about the benefits of self-monitoring. They will complete daily symptoms surveys as part of routine clinical care while attending the BHP and will complete optional weekly symptom surveys, as well as the EMA, during the month post-discharge via the MetricWire app. Additionally during the Long Term phase, months 2 and 3 post discharge, participants can complete weekly symptom monitoring surveys as desired.

Symptom Tracking Treatment phase	Location	Frequency of sessions	Duration
Acute (1 to 14 days)	Hospital	No additional treatment, self-monitoring as part of TAU	na
Transition (1-month)	Home	4x daily affect surveys as well as weekly symptom monitoring survey	15 min/day
Long-Term (2 mo)	Home	Symptom monitoring surveys as desired	2min/week

If under any circumstance in-person assessments are not possible, all study assessments and procedures can be completed remotely via telephone, encrypted email, or video-call, depending on the preference of the participant (see Risks and Discomforts section). Additionally, in cases of remote recruitment, participants will be screened over the phone and will be sent the assessment version of the WSAP (see measures) to assess eligibility prior to consent.

**Retention.** Post-discharge, staff will monitor participants' progress with the HabitWorks app and MetricWire app and will call participants who have not completed any sessions in either app over the past week. They will monitor this each week for the month of transition phase. The purpose of these phone calls will be to help identify barriers and brainstorm potential solutions. To increase retention, we will: a) obtain contact information of individuals who will always know how to reach participants; b) pay participants for assessments; and c) provide transportation if needed, flexible scheduling for the assessments, and in rare individual cases conduct interviews via telephone. In the event that a participant is unable to attend follow-up assessments, or follow-up assessments are not occurring in person, we will conduct the entire assessment through remote methods such as encrypted email, phone call, and video call. We will follow these procedures for both treatment conditions.

